## 1 List of Abbreviations

ADR	Adverse Drug Reaction
AE	Adverse Event
cFGF23	C-terminal Fibroblast Growth Factor 23
CI	Confidence Interval
CMH	Cochran-Mantel-Haenszel
CRF	Case Report Form
CSR	Clinical Study Report
CTX	Carboxy-terminal Collagen Crosslinks
ECG	Electrocardiogram
FACIT	Functional Assessment of Chronic Illness Therapy
FAS	Full Analysis Set
Hb	Haemoglobin
IDA	Iron Deficiency Anaemia
iFGF23	Intact Fibroblast Growth Factor 23
ITT	Intention-To-Treat
LLOQ	Lower Limit Of Quantification
MCS	Mental Component Summary
MedDRA	Medical Dictionary for Regulatory Activities
MEP	Maximal Expiratory Pressure
MIP	Maximal Inspiratory Pressure
MMRM	Mixed Models for Repeated Measures
PCS	Physical Component Summary
PINP	Propeptide of Type I Collagen
PP	Per Protocol

Sponsor:	Pharmacosmos A/S	Date:	12MAR2018
Drug/Project:	Monofer	Version:	Final 2.0
Trials:	P-Monofer-IDA-04 P-Monofer-IDA-05	Statistical Analysis Plan	

PT	Preferred Term
PTH	Parathyroid Hormone
QoL	Quality of Life
REML	Restricted Maximum Likelihood
SAE	Serious Adverse Event
SAP	Statistical Analysis Plan
SAR	Serious Adverse Reaction
SD	Standard Deviation
SF-36	Short Form - 36
S-ferritin	Serum-ferritin
SMQ	Standardised Medical Dictionary for Regulatory Activities Query
SOC	System Organ Class
S-phosphate	Serum-phosphate
SUSAR	Suspected Unexpected Serious Adverse Reaction
TEAE	Treatment Emergent Adverse Event
TSAT	Transferrin Saturation
VAS	Visual Analogue Scale

Sponsor:	Pharmacosmos A/S	Date:	12MAR2018
Drug/Project:	Monofer	Version:	Final 2.0
Trials:	P-Monofer-IDA-04 P-Monofer-IDA-05	Statistical Analysis Plan	

## 2 Introduction

The generic statistical analysis plan (SAP) for the identical trials P-Monofer-IDA-04 and P-Monofer-IDA-05 is based on the final protocols, both version 3.0 including amendment 2 dated 29 November 2017.

Reporting of each trial will be done individually after the date of last subject last visit of the trials.

A combined analysis is planned, which will be done when both trials are finalised. The trials will be reported without the combined analysis, which will be included as an appendix to both clinical study reports (CSRs).

The SAP describes in detail the analyses to be conducted and highlights any deviations from the analysis described in the protocols (see section 8). Deviations from methods described in this SAP, if any, will be specified in the CSRs.

Before releasing data for final analysis, one or more data review and classification meeting will be held to review protocol deviations in order to classify subjects with respect to analysis populations. The product of the classification meetings will be a detailed description of the analysis populations, and the number and nature of unresolved data queries will also be reported.

The analysis is performed based on:

- The clinical database, which includes the electronic Case Report Forms (CRF)
- List of protocol deviations
- Analysis populations documented in the data base lock minutes.

Sponsor:	Pharmacosmos A/S	Date:	12MAR2018
Drug/Project:	Monofer	Version:	Final 2.0
Trials:	P-Monofer-IDA-04 P-Monofer-IDA-05	Statistical Analysis Plan	

### 3 Trial Characteristics

#### 3.1 Trial Objectives

##### 3.1.1 Primary objective

The primary objective of the trials is to compare the incidence of hypophosphatemia in subjects with Iron Deficiency Anaemia (IDA) treated with iron isomaltoside or ferric carboxymaltose.

##### 3.1.2 Secondary safety objectives

The secondary safety objectives of the trials are to compare the effects of iron isomaltoside and ferric carboxymaltose treatment in subjects with IDA on the following:

- (1) Incidence of severe hypophosphatemia
- (2) Time with hypophosphatemia
- (3) Proportion of subjects with hypophosphatemia at the last visit
- (4) Absolute [Δ] and relative [%] changes in serum-phosphate (s-phosphate)
- (5) Fractional phosphate urinary excretion
- (6) Intact Fibroblast Growth Factor 23 (iFGF23), C-terminal FGF23 (cFGF23), vitamin D (25, 1.25, 24.25), Parathyroid Hormone (PTH), and ionized calcium
- (7) Adverse Events (AEs) and biochemical safety parameters

##### 3.1.3 Secondary efficacy objectives

The secondary efficacy objective of the trials is to compare the effects of iron isomaltoside and ferric carboxymaltose treatment in subjects with IDA on Haemoglobin (Hb), serum-ferritin (s-ferritin), and Transferrin Saturation (TSAT).

##### 3.1.4 Additional objectives

In addition to the trials primary and secondary objectives, the effect of iron isomaltoside and ferric carboxymaltose will be investigated purely exploratory on the following:

- (1) Biochemical bone/muscle markers
- (2) Fatigue symptoms
- (3) Quality of Life (QoL)
- (4) Bone pain
- (5) Muscle strength

Sponsor: Pharmacosmos A/S	Date: 12MAR2018	
Drug/Project: Monofer	Version: Final 2.0	
Trials: P-Monofer-IDA-04 P-Monofer-IDA-05	Statistical Analysis Plan	

### 3.2 Trial Design

The trials are randomized, open-label, comparative trials. The trials duration for the individual subjects will be approximately 9 weeks (including a 28 days screening period) and each subject will attend 8 visits. Subjects with IDA will be stratified according to type of underlying disease (women with IDA due to gynaecological blood losses; yes/no) and screening s-phosphate level (< 3.5 mg/dL or  $\geq$  3.5 mg/dL), and randomized 1:1 to one treatment course of one of the following treatments:

- Group A: iron isomaltoside (1000 mg infusion at baseline, cumulative dose: 1000 mg)
- Group B: ferric carboxymaltose (750 mg infusion at baseline and day 7, cumulative dose: 1500 mg)

It is intended that 50 % of the recruited subjects are women with IDA due to gynaecological blood losses.

**Table 1: Activities Flow Chart**

Visit	1 Screening	2 Baseline	3	4	5	6	7	8
Time (days)	Max -28	0	1	7	8	14	21	35
Visit window (days)	-	-	+1	+1	+1	$\pm 2$	$\pm 3$	$\pm 3$
Informed consent	X							
Demographics	X							
In/exclusion criteria	X	X						
Eligibility lab tests a	X							
Pregnancy test, if relevant		X						
Medical history		X	X	X	X	X	X	X
Concomitant medication		X	X	X	X	X	X	X
Physical examination		X b						X
Height b		X						
Weight		X b						X
Vital signs c		X		(X)				
Randomization		X						
ECG c		X	X	X	X	X	X	X
FACIT Fatigue Scale		X				X		X
SF-36 questionnaire		X				X		X
Bone pain intensity/VAS		X				X		X
Grip strength/Jamar hand dynamometer		X				X		X

Sponsor: Pharmacosmos A/S	Date: 12MAR2018
Drug/Project: Monofer	Version: Final 2.0
Trials: P-Monofer-IDA-04 P-Monofer-IDA-05	Statistical Analysis Plan
Statistical Analysis Plan	

Visit	1 Screening	2 Baseline	3	4	5	6	7	8
Time (days)	Max -28	0	1	7	8	14	21	35
Visit window (days)	-	-	+ 1	+ 1	+ 1	± 2	± 3	± 3
1 kg arm lift test		X				X		X
30 sec chair stand test		X				X		X
MIP and MEP		X				X		X
Vitamin E		X						
Safety lab tests		X	X	X	X	X	X	X
Efficacy lab tests		X	X	X	X	X	X	X
Exploratory lab tests		X	X	X	X	X	X	X
Urine sample		X	X	X	X	X	X	X
Treatment with iron isomaltoside d or		X						
Treatment with ferric carboxymaltose d		X		X				
Adverse events		X	X	X	X	X	X	X
Final visit form e								X

- a. If the subject's Hb value is unknown to the Investigator, pre-screening with HemoCue Hb test may be performed.
- b. Physical examination, height, and weight may be measured between the screening and baseline visit.
- c. For details of the assessment, please see the protocol Sections 7.8 (vital signs) and 7.9 (ECG).
- d. All trial assessments should be done before administration of the trial drug unless otherwise stated in the protocol Section 7.
- e. The final visit form may be filled in at any time of the trial if the subject is withdrawn.

### 3.3 Subject included

#### 3.3.1 Sample Size Determination

Data from a previous trial conducted with iron isomaltoside 1000 mg suggests that the incidence of hypophosphatemia in a gynaecology population with/without heavy uterine bleeding can be expected to be approximately 10 % (P-Monofer-IDA-01, 1000 mg; n=3/29=10.3 %, 95 % Confidence Interval (CI) = 2-27 %, gynaecology subgroup; n = 1/10 = 10.0 %, 95 % CI = 0-45 %). For ferric carboxymaltose, the incidence has been observed to be 40-70 % (e.g. Wolf *et al.*, 2013; n = 10/17 = 59 %, 95 % CI = 33-82 %). The significance level is set to 5 %, and the power is set to 80 %. Assuming incidences of 15 % for iron isomaltoside and 40 % for ferric carboxymaltose, 49 subjects in each treatment group is required to detect a difference between the treatment groups.

To account for the uncertainty, and to gain more safety information, 60 subjects per treatment group will be randomized in both trials.

## 4 Analysis Populations

The following data analysis sets are defined in the protocol:

- Intention to Treat (ITT) analysis set: The ITT analysis set will include all randomized subjects. This will be the primary analysis set for evaluating efficacy. Subjects will be included as randomized.
- Safety analysis set: The safety analysis set will include all subjects who received at least one dose of the trial drug. This will be the analysis set for evaluating safety. Subjects will be included as treated.
- Full Analysis Set (FAS): The FAS will consist of all randomized subjects who received at least one dose of the trial drug and have at least one post baseline Hb assessment. Subjects will be included as randomized.
- Per Protocol (PP) analysis set: The PP analysis set will include all subjects in the FAS who do not have any major protocol deviation of clinical or statistical significance. Major protocol deviations are defined in the trial protocols Section 17.3.

The primary analysis population is the safety analysis set, which will be used for all safety evaluations. ITT analysis set will be used for all efficacy evaluations. FAS and PP analysis set will be used for the analysis of Hb.

## 5 Planned Statistical Methods

### 5.1 Statistical Considerations

Baseline is defined as the last assessment with available data prior to the first administration of trial medication. The following visits are scheduled:

**Table 2 Visit schedule**

Visit	1 Screening	2 Baseline	3	4	5	6	7	8
Time (days)	Max -28	0	1	7	8	14	21	35
Visit window (days)	-	-	+ 1	+ 1	+ 1	± 2	± 3	± 3

The visits will be labelled by screening, baseline and scheduled day. Categorical data will be summarized by treatment, using number and percentages of subjects. For calculation of percentages, the denominator will either be the number of subjects in the analysis set or the number of subjects in the analysis set with non-missing values. Continuous data will be presented using the number of subjects (n), mean, standard deviation (SD), median, lower quartile, upper quartile, minimum and maximum. Both the absolute values and the change from baseline will be presented.

Sponsor:	Pharmacosmos A/S
Drug/Project:	Monofer
Trials:	P-Monofer-IDA-04 P-Monofer-IDA-05

Date:	12MAR2018
Version:	Final 2.0
Statistical Analysis Plan	

Descriptive statistics for all endpoints will be presented by treatment group and day, if applicable, using observed cases, i.e. no imputation of missing data will be performed. Missing data for time to event endpoints is handled using censoring.

Values below lower limit of quantification (LLOQ) will be substituted by 0.5\*LLOQ in tables and figures.

In the following, strata are defined as *Type of underlying disease: women with IDA due to gynaecological blood losses (yes or no) and screening s-phosphate level (< 3.5 mg/dL or ≥ 3.5 mg/dL)*.

### 5.1.1 Key methods

The following two methods will be used for several endpoints.

#### Cochran-Mantel-Haenszel

Iron isomaltoside will be compared to ferric carboxymaltose by estimation of the risk difference of a parameter and the associated 95 % Newcombe CI adjusting for strata using the Cochran-Mantel-Haenszel (CMH) method. The risk difference, 95 % CIs and the corresponding p-value will be presented.

#### Mixed Models for Repeated Measures

Change in a parameter from baseline will be analysed using a Restricted Maximum Likelihood (REML)-based Mixed Models for Repeated Measures (MMRM) approach. All subjects with post-baseline data will be included with their observed data. Subjects without post-baseline values will have change from baseline set to 0 at the first post-baseline visit.

The model will include the fixed, categorical effects of treatment (iron isomaltoside and ferric carboxymaltose), strata, day, treatment-by-day interaction, as well as the continuous, fixed covariates of the parameters baseline value and baseline value-by-day interaction. An unstructured covariance matrix will be used to model the within-subject errors. If, unexpectedly, this analysis fails to converge, the following structures will be applied, in the following order; first-order ante-dependence, heterogeneous compound symmetry, compound symmetry. The comparisons will be the contrasts between iron isomaltoside and ferric carboxymaltose at the day or days in question based on the least squares means for the treatment-by-day interaction effect. The estimated mean differences based on this model will be reported with two-sided symmetric 95 % CIs and corresponding p-values. The Kenward-Roger approximation will be used to estimate the denominator degrees of freedom.

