Plots including the Kaplan-Meier curves, log-rank test and median time with hypophosphatemia will be presented overall by treatment. All periods will be presented by subject in a swimmer plot.

### 7.2.3 Proportion of hypophosphatemia at day 35

The proportion of subjects with hypophosphatemia at day 35 will be analysed and presented like the primary endpoint using the CMH described in section 5.1.1. for observed cases only.

The number and percentage of subjects with hypophosphatemia will be summarised by treatment and listed by subject as described in section 7.1.1.

### 7.2.4 Absolute [Δ] and relative [%] changes in s-phosphate from baseline to day 1, 7, 8, 14, 21, and 35

The change in s-phosphate from baseline to day 1, 7, 8, 14, 21, and 35 will be analysed and presented using the MMRM described in section 5.1.1.

The change in s-phosphate will be summarised by treatment and visit, and mean plot of absolute change over time will be presented.

The percentage change in s-phosphate from baseline to day 1, 7, 8, 14, 21, and 35 will be analysed and presented using the MMRM described in section 5.1.1.

The percentage change in s-phosphate will be summarised by treatment and visit, and mean plot of percentage change over time will be presented.

### 7.2.5 Fractional phosphate urinary excretion at day 1, 7, 8, 14, 21, and 35

The fractional phosphate urinary excretion at day 1, 7, 8, 14, 21, and 35 including change from baseline will be summarised by treatment and visit. All data will be listed by subject.

Sponsor: Pharmacosmos A/S	Date: 12MAR2018	
Drug/Project: Monofer	Version: Final 2.0	
Trials: P-Monofer-IDA-04 P-Monofer-IDA-05	Statistical Analysis Plan	

## 7.2.6 Change in iFGF23, cFGF23, vitamin D (25, 1.25, 24.25), PTH, and ionized calcium from baseline to day 1, 7, 8, 14, 21, and 35

The change in each of the following 7 endpoints

- iFGF23
- cFGF23
- vitamin D (25)
- vitamin D (1.25)
- vitamin D (24.25)
- PTH
- ionized calcium

from baseline to day 1, 7, 8, 14, 21, and 35 will be analysed using the MMRM described in section 5.1.1..

A summary of absolute values and change from baseline by treatment and visit, and mean plots of change over time will be presented for each endpoint. All data will be listed by subject.

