## 7.6 Handling of Missing Values

For the primary endpoint, the first post-baseline s-phosphate measurement is taken at day 1, hence, very few missing values are expected. If there are subject(s), for whom no post-baseline s-phosphate

Sponsor:	Pharmacosmos A/S	Date:	12MAR2018
Drug/Project:	Monofer	Version:	Final 2.0
Trials:	P-Monofer-IDA-04 P-Monofer-IDA-05	Statistical Analysis Plan	

measurement(s) are available, these subjects will be set as having s-phosphate < 2 mg/dL in the primary analysis.

In the MMRM analyses subjects without post-baseline values will have change from baseline set to 0 at the first post-baseline visit.

Missing values for the SF-36 questionnaires will be handled using the Half-scale rule, i.e. a score will be calculated if at least 50 % of the items are answered by a subject at a given visit. The missing items will be imputed by the average score of the non-missing items. The PCS score can be computed if at least seven scales have been scored, one of which being the PF scale; similarly, the MCS score can be computed if at least seven scales have been scored, one of which being the MH scale.

Besides from this no imputation of missing values will be applied.

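### The MMRM enters an invented zero change as if observed for subjects with no post-baseline value, and the nine secondary safety MMRMs have no fit without it

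*SAP*

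**What the plan says.** SAP section 5.1.1 (Mixed Models for Repeated Measures) enters subjects who have post-baseline data with what was observed, then adds: "Subjects without post-baseline values will have change from baseline set to 0 at the first post-baseline visit". Section 7.6 restates this without restriction: "In the MMRM analyses subjects without post-baseline values will have change from baseline set to 0 at the first post-baseline visit". After the SF-36 rules, it closes with "Besides from this no imputation of missing values will be applied".

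This MMRM is used for nine secondary safety endpoints. Section 7.2.4 covers absolute s-phosphate change ("The change in s-phosphate from baseline to day 1, 7, 8, 14, 21, and 35 will be analysed and presented using the MMRM") and percentage change. Section 7.2.6 adds iFGF23, cFGF23, three vitamin D forms, PTH and ionized calcium. It is also used for Hb per gram iron, s-ferritin and TSAT (section 7.3) and for the exploratory endpoints (section 7.5).

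Section 4 defines the safety set by dosing alone. The FAS also requires a post-baseline Hb value, and the PP set is a subset of the FAS. Their use is limited: "FAS and PP analysis set will be used for the analysis of Hb". Section 5.1 plans descriptive statistics "using observed cases, i.e. no imputation of missing data will be performed".

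For the primary endpoint, section 7.6 treats subjects with no post-baseline s-phosphate differently: "these subjects will be set as having s-phosphate < 2 mg/dL in the primary analysis".

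**The concern.** An MMRM fitted to observed data needs no value for a subject who has none; that subject adds no information about change. Entering a zero does two things. It moves the arm's first-visit mean towards no change, and it counts the subject as measured, so the standard error ignores that the value was invented.

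For the safety parameters the rule has no dependable direction. It understates the first-visit change in any arm that holds zeros, and the treatment contrast may shrink or grow depending on which arm that is. No planned model would show a reader the secondary safety results without it.

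The two s-phosphate MMRMs also sit awkwardly beside the primary analysis. A dosed subject with no follow-up s-phosphate is taken as unchanged in the first and as hypophosphatemic in the second. These are different endpoints, so this is an inconsistency of assumptions and not two rules for one analysis.

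**Working it through.** **Which models have a fit without the zero**

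| Endpoints | Analysis set | Fit without the zero |
|---|---|---|
| Secondary safety: 2 s-phosphate + 7 markers = 9 | Safety (section 7) | None |
| Hb per gram iron | ITT, FAS, PP (section 7.3.1) | Yes: FAS and PP |
| s-ferritin, TSAT | ITT (section 7) | None |

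The sensitivity analyses in section 7.1.1 are a logistic regression and Fisher's exact test. They serve the primary endpoint and, through section 7.2.1, the incidence below 1.0 mg/dL. None concerns an MMRM.

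In 17 exploratory models the first post-baseline visit is day 14, one of only two analysed visits: FACIT 1 + SF-36 10 (8 domains, PCS, MCS) + bone pain 1 + grip strength 1 + limb tests 2 + MIP and MEP 2 = 17.

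**Shift in the mean.** The SAP gives no count of affected subjects, so the counts below are assumptions. Take n = 60 per arm (section 3.3.1) and k zeros. The arm mean becomes (1 - k/n) times the observed mean, a shrinkage of k/n: 1/60 = 1.7%, 3/60 = 5.0%.

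**Shift in the contrast.** Assume observed day-1 changes in s-phosphate of -0.2 mg/dL (iron isomaltoside, A) and -0.6 mg/dL (ferric carboxymaltose, B). Neither value is in the SAP. Without zeros, A - B = 0.40. With zeros:

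A - B = (1 - kA/60)(-0.2) - (1 - kB/60)(-0.6)

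- kA = 1, kB = 1: -0.1967 + 0.5900 = 0.393
- kA = 3, kB = 3: -0.19 + 0.57 = 0.380
- kA = 3, kB = 0: -0.19 + 0.60 = 0.410
- kA = 0, kB = 3: -0.20 + 0.57 = 0.370

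**Standard error.** This is an unadjusted two-sample approximation with assumed SD s. For an arm with observed mean m, the variance with k zeros is

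[(n - k - 1)s² + (n - k)(k/n)m²] / (n - 1),

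divided by n for the mean. The observed-data counterpart is s²/(n - k).

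Example with three zeros per arm and s = 0.6:

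- Arm A: (56 × 0.36 + 57 × 0.05 × 0.04)/59 = 0.3436
- Arm B: (56 × 0.36 + 57 × 0.05 × 0.36)/59 = 0.3591
- SE with zeros: √[(0.3436 + 0.3591)/60] = 0.1082
- SE from observed data: √(2 × 0.36/57) = 0.1124
- Ratio: 0.963

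| Zeros (A, B) | Contrast | SE ratio, SD 0.4 | SD 0.5 | SD 0.6 |
|---|---|---|---|---|
| 1, 1 | 0.393 | 0.994 | 0.990 | 0.988 |
| 3, 3 | 0.380 | 0.979 | 0.969 | 0.963 |
| 0, 3 | 0.370 | 1.001 | 0.992 | 0.987 |

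The standard error is 0.6 to 1.2% too small with one zero per arm and 2.1 to 3.7% too small with three per arm. With three zeros only in the arm with the larger change, it runs from slightly more than 1% too small to 0.1% too large.

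**The case against.** The strongest reply is that the rule will hardly ever operate. For the nine safety endpoints a subject must lack a value at every one of days 1, 7, 8, 14, 21 and 35. The safety set holds only dosed subjects, and for s-phosphate section 7.6 says "hence, very few missing values are expected". If nobody qualifies, the planned MMRM already is the observed-data fit.

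When zeros are balanced, the estimate and its standard error shrink together. In the illustration, contrast divided by standard error falls by about 0.5 to 1.0% with one zero per arm and 1.3 to 3.0% with three. Larger movements, about 5 to 8% in either direction, need three such subjects in one arm and none in the other, and nothing in the SAP suggests that. Observed-case summaries and subject listings would show the raw means and let a reader find the affected subjects. The secondary p-values carry no multiplicity control, and the 17 two-visit models are exploratory.

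All of this stands as an argument about weight, and it keeps the point minor. It does not defend the rule. Descriptive tables give no adjusted contrast. The expectation of few missing values is stated for the primary endpoint because sampling starts at day 1. That reasoning does not extend to measures first taken at day 14, or to s-ferritin and TSAT in an ITT set that includes randomized subjects who were never dosed.

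**Conclusion.** The point holds and is minor. Whenever the rule is triggered, it biases the within-arm first-visit change towards zero by k/n and usually makes the standard error too small. The nine secondary safety MMRMs, and s-ferritin and TSAT, have no planned fit that avoids it.

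That the rule exists and that no companion fit is planned follow directly from the text. The size rests on assumed counts, mean changes and SDs, and on an unadjusted approximation to a model that also adjusts for baseline, strata and day. Only the first post-baseline visit is claimed here; nothing is rested on later days. The primary CMH analysis and the sample size are unaffected.

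**What to change.** - **Safety-set and exploratory MMRMs:** delete the zero-change sentence from sections 5.1.1 and 7.6 and fit observed post-baseline data only.
- **ITT efficacy endpoints (Hb per gram iron, s-ferritin, TSAT):** make the observed-data fit the main analysis. Keep the zero-change version, if wanted, as a labelled sensitivity analysis.
- **Reporting:** give the number of subjects with no post-baseline value, by arm and endpoint.

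The pooled analysis in section 7.10 follows the individual-trial methods, so it should take the same change.

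The cost is one sentence edited in two places and one short count table. Programming falls where the rule is dropped. Keeping the zero version for the three efficacy endpoints means a second fit for each. The downside is that a few subjects contribute no outcome row to the model.
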